6.2.2.2. Duration of CR, and Durations of Response

For the time-to-event endpoints of DCR and DOR, analyses will be conducted based on the subsets on which the outcome measures are defined. Specifically, DCR will be based on patients who achieve CR, and DOR will be based on patients who achieve objective response. The Kaplan-Meier method will be used to estimate median duration with its 95% CI, and Kaplan-Meier plots will be provided. The censoring rules for DCR and DOR are summarized in Table 6-1.

6.2.2.3. Event-Free Survival, Time to Transformation to AML, and Progression-Free Survival

The distribution of EFS, time to transformation to AML, and PFS will be estimated for each treatment arm using Kaplan-Meier method and compared between treatment arms using the stratified log-rank test, stratified by the stratification factors at randomization for the ITT Analysis Set. Medians, Q1, Q3 of the distributions, and the proportion of patients who are event-free at 6, 12, 18 and 24 months from randomization will be estimated along with corresponding 95% CIs using the Kaplan-Meier method. Kaplan-Meier curves will be provided by treatment group. The hazard ratio between treatment arms will be estimated using the Cox proportional hazards regression model stratified by the stratification factors. The censoring rules for EFS, Transformation to AML, and PFS are summarized in Table 6-2.

6.2.2.4. RBC Transfusion Independence Rate

The point estimates of RBC transfusion independence rate as well as the corresponding 2-sided exact 95% CIs based on Clopper-Pearson method will be provided by treatment arm respectively. Estimation will be based on a subset of all randomized patients who are RBC transfusion dependent at baseline. Difference in transfusion independence rate between treatment groups will be tested using the Cochran-Mantel-Haenszel test, stratified by the randomization stratification factors.

Table 6-1.Censoring Rules for DCR, DOR, and Duration of RBC TransfusionIndependence

Situation	Date of Censoring	
No subsequent response assessments and no death after the first date CR/OR/RBC transfusion independence met	Date of first time meet CR/OR/RBC transfusion independence	
No corresponding events or no subsequent response assessments on or prior to initiation of any new anticancer therapy (excluding SCT)	Date of the last response assessment on or before the initiation of the new anticancer therapies (excluding SCT) or Date of first time meet CR/OR/RBC transfusion independence	
No corresponding events and no any new anticancer therapy (excluding SCT)	Date of the last response assessment	

Table 6-2. Censoring Rules for EFS, Time to Transformation to AML, and PFS

Situation	Date of Censoring	
No postbaseline response assessment (for Time to Transformation to AML);	Date of randomization	
No postbaseline response assessment and no death (for EFS and PFS)		
No corresponding events or no postbaseline response assessment on or prior to initiation of any new anticancer therapy (excluding SCT)	Date of the last response assessment on or before the initiation of the new anticancer therapies (excluding SCT) or date of randomization	
No corresponding events and no any new anticancer therapy (excluding SCT)	Date of the last response assessment	

6.3. Exploratory Efficacy Endpoints

6.3.1. Definition of Exploratory Efficacy Endpoints

Duration of RBC Transfusion Independence: The duration of RBC transfusion independence is measured from the time the assessment criteria are first met for RBC transfusion independence until RBC transfusion dependence again (including assessments post SCT) or death, whichever occurs first. Those who are not observed to have RBC transfusion dependence again or death will be censored at the date of their last response assessment. If patients start taking new anticancer therapies (excluding SCT) before becoming RBC transfusion dependent again or death, duration of RBC transfusion independence will be censored at the last response assessment on or before the initiation of the new anticancer therapies (excluding SCT).

Transplantation Rate: The transplantation rate is the proportion of patients who initiated transplant type subsequent anti-cancer therapy for MDS.

Time to First Transplant: Time to first transplant is defined as the time from randomization to the initiation of first transplant type subsequent anti-cancer therapy for MDS. The definition has been changed from protocol definition. Specifically, time to first transplant will just be based on participants who had initiated transplant. Participants who are not observed to initiate transplant will be excluded.

RBC Transfusion Independence Rate Irrespective of RBC Transfusion Status at Baseline: The RBC transfusion independence rate irrespective of RBC transfusion status at baseline is the proportion of patients who have a 56-day or longer period with no RBC transfusions at any time between randomization and initiation of any new anticancer therapy, including SCT, among all randomized patients.

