Abbreviations: CBC = complete blood count; EQ-5D-5L = 5-level EuroQol 5 dimensions; FACT-Anemia = Functional Assessment of Cancer Therapy-Anemia; MRD = minimal residual disease; PGIC = Patient Global Impression of Change; PGIS = Patient Global Impression of Severity; PRO = patient-reported outcome; Q2C = every 2 cycles; Q3C = every 3 cycles.

- a Four PRO questionnaires will be administered in this study: the FACT-Anemia questionnaire, the EQ-5D-5L, the PGIS, and the PGIC. The participant should complete these questionnaires before other study procedures at required visits. No PGIC assessment at Cycle 1 Day 1. FACT-Anemia and EQ-5D-5L should be implemented prior to PGIS/PGIC.
- b If magrolimab and azacitidine are administered on the same day, only one such study assessment is needed. Assessments should be performed prior to study treatment administration. Pretreatment assessments for the initial dose (Cycle 1 Day 1) may be collected up to 72 hours before administration of study treatment; thereafter, pretreatment assessments are to be collected within 24 hours prior to study treatment administration.
- c Bone marrow biopsy samples will be collected at Day 1 of Cycles 3 and 10.
- d An aspirate sample will be collected for response assessment, biomarker studies, and MRD assessment. Conventional cytogenetics to be tested per institutional standards. Response assessments may be adjusted by ± 1 week for Cycle 3 Day 1. After Cycle 3 Day 1, the window is ± 14 days.
- e An aspirate sample will be collected for biomarker studies at Day 1 of Cycles 3, 5, 7, 10, and 13.
- f Samples will be collected at Day 1 of Cycles 3, 5, and 7 and then every 3 cycles thereafter during study treatment. Bone marrow aspirate biopsies for response assessments may be adjusted by ± 1 week for Cycle 3 Day 1. After Cycle 3 Day 1, the window is ± 14 days.
- g Vital signs will be assessed prior to infusion/injection of each study treatment. Weight will be assessed on Day 1 of each cycle. Details are provided in Section 5.1.5.
- h If azacitidine and magrolimab/placebo are administered on the same day, azacitidine administration should be completed at least 1 hour before magrolimab/placebo administration. Azacitidine may be administered on an alternative schedule of Days 1 to 5, Day 8, and Day 9 of a 28-day cycle for flexibility and convenience.

Table 4. Schedule of Assessments - Treatment Period-Magrolimab or Placebo Dosing and Study Assessments

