- f Response assessment at EOT visit not required if performed within the last 30 days or progressive disease has been documented. After disease progression (including treatment failure by IWG criteria and relapse after CR or PR), response assessment will focus on evaluation of transformation to AML.
- g Paper PROs will be administered in this study: The FACT-Anemia questionnaire, the EQ-5D-5L, the PGIS, and the PGIC will be administered. The participant should complete these questionnaires before other study procedures at required visits. FACT-Anemia and EQ-5D-5L should be implemented prior to PGIS/PGIC. FACT-Anemia, EQ-5D-5L, the PGIS, and the PGIC should also be collected during long-term follow-up prior to initiation disease progression or initiation of a new anticancer therapy.
- h Report all AEs through the Safety Follow-up Visit/Call and any treatment-related SAEs thereafter.
- i Collect blood transfusions until start of new anticancer therapy.
- j Collect new anticancer therapy data following the last dose of study treatment.
- k For participants who do not initiate new anticancer therapy after the last dose. See Section [5.1.10](#) for adverse event reporting details.

Table 6. Schedule of Assessments - Repriming (Required After > 4 Weeks Have Lapsed Since the Last Dose of Magrolimab/Placebo Delays)

Visit Window (Days)	Day										
	1	2	3	4	5	6	7	8	11	15	22
	-	-	± 3	± 3	± 3	± 3	± 3	± 3	± 3	± 3	± 3
Pregnancy test	X										
CBC with differential, platelets, and reticulocytes ^{a,b}	X	X		X				X	X	X	X
Haptoglobin and LDH	X							X			
Serum or plasma chemistry ^a	X							X		X	X
Peripheral smear ^{a,c}	X	X							X		
Peripheral blood for biomarker studies ^d	X							X			
PK ^d	X							X			
Antidrug antibodies ^a	X										
Vital signs ^c	X	X						X		X	X
Symptom-directed physical examination ^a	X							X		X	
Adverse events	X	X	X	X	X	X	X	X	X	X	X
Concomitant medications	X	X	X	X	X	X	X	X	X	X	X
Blood transfusions	X	X	X	X	X	X	X	X	X	X	X
Premedication ^f	X			X				X	X		
Magrolimab/placebo: repriming ^g	X			X				X	X	X	X

Abbreviations: CBC = complete blood count; ECOG = Eastern Cooperative Oncology Group; LDH = lactate dehydrogenase; PK = pharmacokinetic(s); PRO = patient-reported outcome; WBC = white blood cell.

a Pretreatment assessments are to be collected within 24 hours prior to study treatment administration.

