5.3. Efficacy Assessments

Clinical response will be assessed using the guidelines in Appendix B, which are based primarily on IWG criteria {Cheson 2003, Cheson 2006}, as described in Appendix B.

Response assessments will be done in conjunction with bone marrow assessments, according to the Schedule of Assessments (Section 4.3). Accompanying laboratory results \pm 2 weeks from the protocol-specified bone marrow efficacy assessment can be used to support an efficacy assessment of CR. Response assessments are scheduled on Day 1 of Cycles 3, 5, and 7 and then every 3 cycles thereafter during study treatment. These supporting laboratory results will be entered into the clinical database. Absolute neutrophil count, platelets, and hemoglobin, that reflect CR or PR per IWG 2006 criteria (hemoglobin \geq 11 g/dL, platelets \geq $100 \times 10^9/L$, neutrophil \geq $1.0 \times 10^9/L$, peripheral blast = 0%; Appendix B) must be from CBCs collected on the same day. If a participant achieves a CR, subsequent bone marrow biopsies and response assessments are still required to be performed as per the Schedule of Assessments (Section 4.3).

Per Schedule of Assessments during the treatment period (Table 3, and Table 4), treatment cycles are associated with azacitidine dosing. Therefore if azacitidine is delayed, all assessments per Table 3 (e.g., bone marrow aspirate biopsy and MDS disease assessment) will also be delayed until resumption of azacitidine dosing.

Slides used for MDS disease response assessments may be collected by the Sponsor for **CCI** independent pathology review.

Response assessment will be obtained at the EOT Visit, unless a prior response assessment has been performed within the last 30 days or progressive disease has been documented. Response assessments should continue during long-term follow-up approximately every 8 weeks until transformation to AML is documented or start of new anticancer therapy, whichever comes first. For participants who come off the study treatment to receive an SCT, follow-up for response assessment and collection of SOC bone marrow biopsy/aspirate and CBC results will continue until documented relapse or progressive disease occurs. After documented relapse or progressive disease, follow-up for response assessment and collection of SOC bone marrow biopsy/aspirate results will continue until transformation to AML occurs or start of new anticancer therapy, whichever comes first.

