FACT-Anemia Response Rate: The FACT-Anemia response rate is defined as the proportion of participants who showed clinically meaningful improvement in health-related quality of life (HRQoL) based on the score from the FACT-Anemia instrument prior to initiation of any new anticancer therapy, including SCT.

Duration of RBC Transfusion Independence: The duration of RBC transfusion independence is measured from the time the assessment criteria are first met for RBC transfusion independence until RBC transfusion dependence again (including assessments post SCT) or death. Those who are not observed to have one of these events will be censored at the date of their last response assessment with evidence of no RBC transfusion dependence again.

Transplantation Rate: The transplantation rate is defined as the proportion of participants who initiate transplant therapy for MDS after randomization.

Time to First Transplant: Time to first transplant is defined as the time from randomization to the initiation of first transplant therapy for MDS. Participants who are not observed to initiate transplant therapy will be censored at their last known alive date or death date if the patient died.

RBC Transfusion Independence Irrespective of RBC Transfusion-Dependence at Baseline: The RBC transfusion independence irrespective of RBC transfusion-dependence at baseline is the proportion of participants who have a 56-day or longer period with no RBC transfusions at any time between randomization and initiation of any new anticancer therapy, including SCT, among all participants irrespective of RBC transfusion-dependence at baseline.

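### Duration of RBC transfusion independence is censored at the last marrow-based response assessment while later events still count, so SAP 6.3.1 biases it downward, and Table 6-1 does not agree with that text

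*SAP*

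**What the plan says.** **Event.** SAP 6.3.1 runs the duration from the date independence is first met "until RBC transfusion dependence again (including assessments post SCT) or death, whichever occurs first". Nothing in that sentence limits events to dates on or before the last response assessment.

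**Censoring.** Under the same section, patients without an event "will be censored at the date of their last response assessment". For patients who start new anticancer therapy (SCT excepted) before an event, the date is the last response assessment up to that start. SAP 6.3.2 refers to Table 6-1, which this endpoint shares with duration of CR and duration of response. Its first row covers "No subsequent response assessments and no death after the first date CR/OR/RBC transfusion independence met" and sets the censoring date to the day independence was first met.

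**Protocol.** Section 8.4 has event-free patients "censored at the date of their last response assessment with evidence of no RBC transfusion dependence again". The SAP keeps the date and drops the qualifier.

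**When response assessments happen.** Protocol 5.3 ties them to marrow assessments: "Response assessments are scheduled on Day 1 of Cycles 3, 5, and 7 and then every 3 cycles thereafter during study treatment". After treatment they are about every 8 weeks and end at AML transformation or new anticancer therapy.

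**When transfusions are recorded.** Protocol Tables 3 and 4 list transfusions at every treatment visit, and Protocol 6.9.2 provides a dedicated eCRF. For follow-up, Table 5 footnote i says: "Collect blood transfusions until start of new anticancer therapy". SAP 6.3.2 already plans a listing with the date of each transfusion.

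**The concern.** For duration of CR the rule is sensible: relapse is found at a response assessment, so time is credited only as far as the patient was examined. Renewed transfusion dependence and death are learned from other records and at other times. Applying the same rule here means that, after the last marrow, a patient with an event keeps the full duration while a patient without one is moved back to that marrow. Whether the interval counts is decided by what happened in it, which breaks the independent-censoring assumption of Kaplan-Meier. At stake is the median duration reported for each arm, and a rule that two programmers could implement differently because the text and the table do not match.

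**Working it through.** The documents give no expected duration, event count or precision for this endpoint, so there is no plan figure to reproduce.

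**1. Length of the gap.** After Cycle 7, on treatment, assessments are 3 × 28 = 84 days apart. A data cut falling at random in that interval loses on average 84/2 = 42 days of transfusion-free time and at most 84, or 84 + 14 = 98 if the next assessment uses its full window. Between Cycles 3 and 7, and after treatment, the spacing is 56 days: mean 28, maximum 56. The gap is longer if azacitidine is delayed, because Protocol 5.3 delays the marrow with it. It also grows after AML transformation without new therapy, when response assessments stop and transfusion recording does not.

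**2. Mechanism, with two illustrative patients.** Both have their last marrow at month 6 of independence and a data cut at month 8. One becomes dependent at month 7; the other stays independent. Under 6.3.1 the second is censored at month 6, so only one patient is at risk at month 7 and the curve falls from 1 to 0. With known status used, two are at risk and it falls to 1/2.

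**3. Simple simulation.** Assumed: exponential durations, follow-up uniform on 2-24 months, assessments at random phase. Shortfall = 1 − estimate/true median.

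| True median (months) | 12-week gaps | Shortfall | 8-week gaps | Shortfall |
|---|---|---|---|---|
| 8 | 7.6 | 0.4/8 = 5.0% | 7.7 | 0.3/8 = 3.8% |
| 12 | 11.2 | 0.8/12 = 6.7% | 11.5 | 0.5/12 = 4.2% |
| 18 | 16.5 | 1.5/18 = 8.3% | 16.9 | 1.1/18 = 6.1% |

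A large-sample run of the same model gives 5.7-9.0% and 3.8-6.3%, hence about 4-9% overall.

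**4. Simulation on the protocol's on-treatment schedule.** Days 56, 112 and 168, then every 84 days; 400,000 patients per scenario. Assumed: independence first met 56-168 days after randomization, exponential time to event, uniform data cuts, no new therapy. In the early-end columns response assessments stop (median 12 months) while transfusions are still recorded. Entries are estimated medians in months.

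| True median; cut (months) | Known-status censoring | 6.3.1, on schedule | 6.3.1, early end | Row 1 broad, on schedule | Row 1 broad, early end |
|---|---|---|---|---|---|
| 6; 8-20 | 6.00 | 5.76 | 5.26 | 6.55 | 6.04 |
| 6; 8-36 | 6.02 | 5.91 | 5.61 | 6.77 | 6.45 |
| 12; 8-20 | 12.07 | 10.78 | 8.78 | 11.49 | 9.48 |
| 12; 8-36 | 11.99 | 11.56 | 9.89 | 12.40 | 10.71 |
| 18; 8-20 | 17.77 | 14.43 | 11.37 | 14.75 | 12.02 |
| 18; 8-36 | 18.10 | 17.20 | 13.16 | 18.01 | 13.95 |

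The known-status column is from the on-schedule runs. The early-end runs gave 6.00, 6.01, 11.96, 12.02, not reached, and 17.96.

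On schedule, the 6.3.1 shortfall runs from 1 − 5.91/6.02 = 1.8% to 1 − 14.43/17.77 = 18.8%. The largest value arises where the median lies near the end of observable follow-up. With early end it runs from 1 − 5.61/6.01 = 6.7% to 1 − 13.16/17.96 = 26.7%. The 6.3.1 rule was short in all 12 scenarios.

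**5. Table 6-1, row 1.** Two readings are possible.
- *Narrow:* the row applies only to patients with no later assessment at all. The results in step 3 are then essentially unchanged.
- *Broad:* any non-fatal event before the next assessment is replaced by censoring at day zero. This is the last two columns in step 4: above the true median in all four runs with a true median of 6 months and in one run at 12, about equal to it in one run at 18 (18.01), and still short in the other six.

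On either reading, a patient with no later marrow gets zero duration despite months of documented transfusion-free time.

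**The case against.** A reader might infer that the plan understates durations whatever rule is followed. The documents do not support that. SAP 6.3.2 names Table 6-1 as the censoring rule, and its first row exempts only death. The downward direction therefore rests on the 6.3.1 text, and a broad reading of the row can offset or reverse it. This part of the objection stands.

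A reader might also infer that transfusion status is known continuously. Recording is tied to the start of new anticancer therapy, and for patients who start it, events after the start are excluded along with later event-free time. In Protocol Table 5 the transfusion row is blank at the end-of-treatment, 30-day and 70-day contacts, although footnote i supports collection over that period. The form records transfusions given, not a dated confirmation that none was given. Neither document defines renewed dependence operationally for this endpoint; the only transfusion-based response criterion, HI-E, compares 8-week periods. These gaps limit the precision of any fix, but they do not make the marrow date the right one.

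The protocol itself names the last response assessment, so the SAP did not invent the date. That is correct, and it means both documents need attention.

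Finally, the effect is small beside sampling error. With an assumed 40 to 130 patients achieving independence per arm and a true median of 12 months, the estimated median would range over roughly 7-19 months (40 patients) or 9-16 months (130). A shift of 0.5 to 0.8 months is well inside that. This limits the weight of the point; a systematic error that is cheap to remove is still worth removing.

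**Conclusion.** The point holds in limited form. Under the 6.3.1 text, censoring depends on outcome for event-free patients without new anticancer therapy, and Kaplan-Meier durations are biased downward. The size is about 4-9% in the simple scenarios, and larger when marrow assessments end before transfusion recording or when the median lies near the end of follow-up. Event times, follow-up and onset of independence are all assumed, so the size is indicative; the direction is not sensitive to those assumptions as long as 6.3.1 governs. Separately, Table 6-1 row 1 can conflict with 6.3.1 by erasing an observed return to dependence.

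It would go too far to infer a biased treatment comparison. Both arms share the rule, the endpoint is exploratory and summarized by arm without a test, and no difference between arms in event rates or in assessment drop-off has been shown. The key secondary transfusion independence rate is a proportion that does not use this censoring date. No primary or key secondary conclusion changes, and the priority is low.

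**What to change.** 1. In SAP 6.3.1, and in a separate Table 6-1 row for this endpoint, count renewed dependence or death as an event whether or not a response assessment precedes or follows it.
2. Censor event-free patients at the last date through which transfusion status is known from the transfusion eCRF or a follow-up contact, no later than the start of new anticancer therapy (SCT excepted).
3. State what establishes that date (for example, the last visit or contact at which transfusions were asked about) and define renewed dependence and its event date.
4. Confirm that transfusion collection continues after SCT. The endpoint includes post-SCT assessments, but Table 5 footnote i does not say whether SCT ends collection.
5. Align Protocol 8.4, or record the departure in SAP Section 10, which now states that there are none.

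The cost is a few lines of text and one derivation. Transfusion dates and follow-up contacts are already collected; the one new element is the definition of the last date with known status. The change should be made before the data for the next analysis are finalized.

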1.1. Study Objectives

The 2 primary objectives of this study are as follows:

- To evaluate the efficacy of magrolimab + azacitidine compared with that of azacitidine + placebo in previously untreated patients with intermediate/high/very high risk myelodysplastic syndrome (MDS) by Revised International Prognostic Scoring System (IPSS-R) as measured by complete remission (CR) rate
- To evaluate the survival benefit of magrolimab + azacitidine compared with that of azacitidine + placebo

The secondary objectives of this study are as follows:

- To evaluate the duration of CR (DCR) of magrolimab + azacitidine compared with that of azacitidine + placebo
- To evaluate the objective response rate (ORR) and duration of response (DOR) of magrolimab + azacitidine compared with that of azacitidine + placebo
- To evaluate red blood cell (RBC) transfusion independence rate of magrolimab + azacitidine compared with that of azacitidine + placebo
- To evaluate the efficacy of magrolimab + azacitidine compared with that of azacitidine + placebo as measured by event-free survival (EFS)
- To evaluate the CR of magrolimab + azacitidine compared with that of azacitidine + placebo in TP53 mutant population
- To assess the level of minimal residual disease (MRD) negativity of magrolimab + azacitidine compared with that of azacitidine + placebo
- To assess time to transformation to acute myeloid leukemia (AML) of magrolimab + azacitidine compared with that of azacitidine + placebo

[figure not shown]
- To evaluate the efficacy of magrolimab + azacitidine compared with that of azacitidine + placebo, as measured by progression free survival (PFS)
- To assess the safety and tolerability of magrolimab + azacitidine compared with that of azacitidine + placebo
- To evaluate pharmacokinetics (PK) of magrolimab
- To evaluate the immunogenicity of magrolimab
- To evaluate the health-related quality of life (HRQoL) of magrolimab + azacitidine compared with that of azacitidine + placebo, as measured by Functional Assessment of Cancer Therapy Anemia (FACT-Anemia) response rate

The exploratory objectives of this study are as follows:

- To evaluate transplantation rate of magrolimab + azacitidine compared with that of azacitidine + placebo
- To assess time to first transplant of magrolimab + azacitidine compared with that of azacitidine + placebo
- To evaluate the duration of RBC transfusion independence of magrolimab + azacitidine compared with that of azacitidine + placebo

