6.3.2. Analysis Methods for Exploratory Efficacy Endpoints

Time to first transplant will be summarized using descriptive statistics by treatment group for patients who are observed to initiate transplant in the ITT Analysis Set.

The duration of RBC transfusion independence will be analyzed in a similar manner as the analysis of DCR, as specified in Section 6.2.2.2. The censoring rule for duration of RBC transfusion independence is summarized in Table 6-1.

The transplantation rate will be analyzed in a similar manner as the analysis of ORR, as specified in Section 6.2.2.1.

A by-subject listing for RBC transfusions required throughout the study will be provided by treatment group and subject ID in chronological order. Date of transfusion, transfusion type, and the number of units transfused will be presented.

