9. PHARMACODYNAMIC ANALYSES

Exploratory analyses may be performed to evaluate the association of each biomarker or combination of biomarkers with clinical outcomes. Additional details will be provided separately by the biomarker sciences group.

10. Changes From Protocol-Specified Analyses

There are no deviations from the protocol-specified analyses.

11. **REFERENCES**

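### The SAP describes time to first transplant only in transplanted participants, so the summary cannot compare the randomized arms on timing, and SAP Section 10 does not record the change from the protocol

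*SAP*

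**What the plan says.** SAP 1.1 lists the exploratory objective: "To assess time to first transplant of magrolimab + azacitidine compared with that of azacitidine + placebo".

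Protocol 8.4 measures the time from randomization and keeps everyone in: "Participants who are not observed to initiate transplant therapy will be censored at their last known alive date or death date if the patient died".

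SAP 6.3.1 departs from this and says so: "The definition has been changed from protocol definition". It continues: "Specifically, time to first transplant will just be based on participants who had initiated transplant", and then: "Participants who are not observed to initiate transplant will be excluded". It gives no reason. SAP 6.3.2 sets the method: "Time to first transplant will be summarized using descriptive statistics by treatment group for patients who are observed to initiate transplant". No Kaplan-Meier or cumulative incidence estimate for this endpoint is planned.

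SAP 6.3.2 also analyses the transplantation rate by arm, in the way used for ORR.

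SAP Section 10 reads: "There are no deviations from the protocol-specified analyses".

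**The concern.** The objective asks whether one randomized arm reaches transplant sooner than the other. The SAP's analysis set is defined by having had the event. Treatment can change who enters that set, through response and through survival, so the two groups described are no longer the randomized groups. Every participant who carries information about not yet being transplanted is removed.

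The median among transplanted participants then depends on when an arm's transplants fall relative to each other, and not on how likely transplant is by a given time. An arm that adds later transplants to the same early ones gets a longer median, and a reader could take this as delay.

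There is also a record-keeping fault. SAP 6.3.1 announces a changed definition, while Section 10, where a reader looks for changes, denies any. The SAP's Introduction promises documentation in the CSR only for changes made after the SAP is final, so that promise does not cover this one.

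**Working it through.** The plan states no transplant rate, effect or precision for this endpoint, so there is no figure of its own to reproduce. The question is whether the planned summary can mislead, and by how much. From the documents: 520 participants randomized 1:1 (260 per arm) and assumed median OS of 18 and 25.4 months (SAP 1.3). All transplant rates and times below are assumptions.

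**Step 1: arithmetic example, 260 per arm.** Control has 20 transplants spread evenly over months 4 to 8. Experimental has 60 spread evenly over months 4 to 16.

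- Rate over months 4 to 8: control 20/4 = 5 per month; experimental 60/12 = 5 per month. The arms are equal at every time up to month 8.
- By month 8: experimental 60 × (8 − 4)/(16 − 4) = 20, so 20/260 = 7.7% in both arms.
- By month 16: experimental 60/260 = 23.1%; control 20/260 = 7.7%. The experimental arm is never behind.
- SAP summary: median (4 + 16)/2 = 10 months for experimental, (4 + 8)/2 = 6 months for control. Experimental looks 4 months slower.

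**Step 2: range over assumptions.** This is a competing-risks simulation with exponential death at the two OS medians, a control transplant hazard of 0.008 per month, and follow-up uniform over 8 to 30 months. Each cell gives control vs experimental.

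| Experimental transplant hazard | Transplanted | SAP median (months) | Cumulative incidence at 6 / 12 / 24 months |
|---|---|---|---|
| Equal to month 6, then 3 times control | 9.8% vs 21.7% | 7.2 vs 9.7 | 4.2 vs 4.4% / 7.4 vs 14.4% / 11.6 vs 27.2% |
| Twice control throughout | 9.8% vs 20.2% | 7.2 vs 7.3 | 4.2 vs 8.5% / 7.3 vs 15.0% / 11.5 vs 23.9% |
| Equal throughout, survival differs | 9.8% vs 10.8% | 7.2 vs 7.7 | 4.2 vs 4.3% / 7.4 vs 7.8% / 11.5 vs 12.9% |

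In the first row, 90% of 4,000 simulated trials of 260 per arm gave the experimental arm both more transplants and a later SAP median. In the second, the hazard doubles and the SAP medians barely differ. In the third, the transplant hazard is identical and the median still moves, because longer survivors stay at risk of a later transplant. The cumulative incidence columns show the right ordering each time.

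**Step 3: how far the data cut matters.** Further inputs from SAP 1.3 are accrual over 22 months and the second interim at 257 deaths. Assume uniform accrual, exponential survival and no loss to follow-up. Expected deaths at month T are the sum over arms of 260 × [1 − (exp(−λ(T − 22)) − exp(−λT))/(22λ)], with λ = ln 2/18 = 0.0385 and ln 2/25.4 = 0.0273.

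- At T = 32.6: control 260 × 0.552 = 143; experimental 260 × 0.437 = 114; total 257.
- Shortest potential follow-up: 32.6 − 22 = 10.6 months.
- Experimental transplants from Step 1 that fall within follow-up: all of months 4 to 10.6, which is 60 × 6.6/12 = 33.0. For months 10.6 to 16, the proportion followed falls from 1 to (32.6 − 16)/22 = 0.755, average 0.877, giving 27 × 0.877 = 23.7. Total 56.7 of 60, about 94%.
- Median among those seen: 4 + (56.7/2)/5 = 9.7 months, against 10 with complete data.

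**The case against.** The strongest reply is that little rides on this. The endpoint is exploratory, absent from the key secondary hierarchy and summarized without a test, and no interim boundary uses it. SAP 6.3.1 discloses the change, and 6.3.2 already calls the summary descriptive and names its subset. The transplantation rate stands beside it: in the Step 1 example the report would show 23.1% against 7.7% next to the two medians, so a reader would not see only a quicker control arm. All of this stands and limits the weight of the point. It does not close the gap, because the rate says how many and not when, and no analysis of timing in all randomized participants remains.

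The size is also fairly challenged. The documents give no transplant rates, and a material reversal needs the hazards to diverge late. With a constant doubling the medians are almost equal, and with survival alone the shift is about half a month.

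Two stronger readings are tempting and are not supported. A reader might infer that the second interim can show only early transplants. On the trial's own planning figures it falls near month 33 with at least 10.6 months of potential follow-up, so late transplants are somewhat under-represented, not invisible. A reader might also infer from exclusion criterion 3 (Protocol 4.8) that transplants can arise only in participants who become candidates after entry. That criterion requires immediate eligibility together with an available donor, so someone already eligible but without a donor can enrol. It also applies to both arms alike and does not itself produce a reversal.

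Finally, Protocol 8.4 gives only a definition with censoring, and Protocol 8.5 names no method for this endpoint. A competing-risks analysis therefore goes beyond restoring the protocol. The reason for preferring it is that Kaplan-Meier with censoring at death would overstate the probability of transplant.

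**Conclusion.** The point holds, as a minor one. The planned summary conditions on a post-randomization outcome, so it cannot answer the between-arm timing objective in SAP 1.1, and SAP Section 10 is wrong as written. Both conclusions rest on the text alone.

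How misleading the summary would be rests on assumed transplant patterns: from 10 against 6 months in the wrong direction when the extra transplants come late, through a near-complete loss of a doubled hazard, to a shift of about half a month from survival alone. It would be wrong to infer that the arm with more transplants must look slower. It can, depending on when the extra transplants occur. Nothing here touches the primary or key secondary conclusions.

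**What to change.** In SAP 6.3.1 and 6.3.2, analyse time to first transplant in the ITT Analysis Set as cumulative incidence by arm. Treat death without transplant as a competing event and censor others at the last known alive date. Give estimates at 6, 12, 18 and 24 months, the landmarks the SAP already uses for OS and EFS. A cause-specific hazard ratio is optional.

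Present this beside the transplantation rate. Keep the summary among transplanted participants, labelled as a description of that subset and not as a comparison of the arms. List the change from Protocol 8.4 in Section 10, with its reason.

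The cost is SAP wording plus one table and one figure, from transplant, death and last-known-alive dates already collected. Participants and sites have nothing extra to do.
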